6.4.1.7. Adverse Events of Interest

Adverse events of interest (AEIs) are defined according to standardized MedDRA queries (SMQs) and/or custom MedDRA queries (CMQs) as specified in

Table 6. A frequency tabulation per AEI by system organ class and preferred term of subjects with TE AEIs by treatment arm will be provided. The custom MedDRA queries search list is provided in Appendix II.

Table 6 Adverse Events of Interest

Adverse Event of Interest	Definition
Major Adverse Cardiovascular Event (MACE)	Event positively adjudicated (see CSP section 10.1.1)
Arterial Systemic Thromboembolic Event (ASTE)	
Venous Thromboembolic Event (VTE)	
Infection	AEs within SOC 'Infections and infestations' with high level group term (HLGT) not equal to 'Ectoparasitic disorders' and 'Helminthic disorders'
Serious Infection	Serious AEs within SOC 'Infections and infestations' with HLT not equal to 'Ectoparasitic disorders' and 'Helminthic disorders'
Opportunistic Infection	All Preferred Terms (PT) within SMQ 20000235, narrow
Malignancy excl. Non-melanoma Skin Cancer	CMQ
Non-melanoma Skin Cancer (NMSC)	CMQ
Gastrointestinal Perforation	CMQ
Herpes Zoster	CMQ
Fracture	All PTs that can be part of the 'Fractures' HLT (n.b. the primary pathway of these terms may be different)

6.4.1.8. Presentation of Results

The analysis will focus on AEs reported during the treatment phase up to the time of ES-confirmed flare. Any AEs reported outside of that period will be listed.

All AE tables will show the number of subjects with applicable TEAEs.

A summary table will be provided, showing the number (percent) of subjects with at least one:

- TEAE,
- serious TEAE,
- TEAE leading to death,
- TEAEs by worst severity,
- IP-related TEAE,
- TEAE leading to study drug interruption,
- TEAE leading to permanent study drug discontinuation,
- TEAE leading to permanent study discontinuation.

Frequency tabulations, by system organ class and preferred term, of the number (percent) of subjects with a TEAE will be presented. Similar tables will be provided for related TEAEs and serious TEAEs.

Serious adverse events, AEs leading to death or leading to study drug discontinuation will be listed.

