9. STATISTICAL METHODS

All statistical methods shall be detailed in a statistical analysis plan (SAP). The SAP will be finalized prior to the interim analysis (see Section 9.3.2) and unblinding. All relevant data collected in this clinical study will be documented using summary tables, figures, and subject data listings.

Any deviations from the CSP are to be justified in the SAP.

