9.3.5. Analyses of Safety Data

All safety analyses will be performed using the safety analysis set (Section 9.2.4). All safety data will be summarized descriptively by treatment group according to the filgotinib dosing regimen actually received at randomization.

For the primary safety analysis, any data collected after ES-confirmed UC flare will not be included in the analyses.

For the secondary safety analysis, data will be included regardless of flare.

Additionally, safety data may be analyzed in the subgroup of subjects who are initially assigned to 100 mg filgotinib q.d. and are re-escalated later to 200 mg q.d. in the safety analysis set.

Missing data for safety endpoints will not be imputed.

Clinical safety will be addressed by assessing AEs, laboratory assessments, physical examinations, ECG, and vital signs.

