2. STUDY DESIGN AND OBJECTIVES

2.1. Study Objectives & Endpoints

Objectives	Endpoints
Primary	
To evaluate the efficacy of filgotinib in subjects in stable clinical remission on 200 mg filgotinib once daily (q.d.) for whom the dose was decreased to 100 mg q.d. compared to subjects remaining on 200 mg q.d.	
– Proportion of subjects in corticosteroid-free^a clinical remission based on modified Mayo Clinical Score (mMCS)^b at Week 48.

^a Free of corticosteroids for at least 12 weeks.

^b mMCS of ≤ 2 points, with endoscopic subscore of ≤ 1 , stool frequency subscore of ≤ 1 , and a rectal bleeding subscore of 0.

Objectives	Endpoints
Secondary	
To evaluate the effect of dose de-escalation of filgotinib on time to flare.	
 – Time to PRO2 flare^c. – Time to endoscopic score (ES)-confirmed ulcerative colitis (UC) flare.
To evaluate the effect of dose de-escalation of filgotinib on disease-specific biomarkers and Inflammatory Bowel Disease Questionnaire (IBDQ).	
 – Change from baseline in C-reactive protein (CRP) and fecal calprotectin (FCP) up to Week 48. – Change from baseline in IBDQ at Week 48.
To evaluate the safety and tolerability of filgotinib.	
 – Frequency and severity of treatment-emergent adverse events (TEAEs), treatment-emergent serious AEs (SAEs), and TEAEs leading to treatment discontinuation.

^c Defined as a PRO2 (patient-reported outcome based on 2 items) score worsening of at least 2 points and an absolute PRO2 score of at least 3, with stool frequency subscore ≥ 2 and rectal bleeding subscore ≥ 1 .

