6. STATISTICAL ANALYSES

6.1. Changes to the Planned Analyses, Not Covered by Protocol Amendments

Due to the termination of the CAPYBARA study and the decision to write an abbreviated CSR, it was decided to limit the analyses to the primary and secondary efficacy endpoints and safety endpoints. Since the study was stopped prior to any subjects reaching the primary analysis time point at Week 48, the analyses described in this SAP will deviate from the planned analyses found in the protocol.

A summary of the modified analyses can be found in [Table 5](#) below.

Table 5 Changes to Planned Analyses

Section SAP	Endpoint	Planned analysis as per Protocol	Revised analysis
PRIMARY ENDPOINTS			
6.3.1	Corticosteroid-free clinical remission based on modified Mayo Clinical Score at Week 48	Treatment difference in the percentage of subjects meeting corticosteroid-free mMCS remission criteria between the filgotinib 100 mg q.d. group and 200 mg q.d. group at Week 48, calculated using Mantel-Haenszel test (stratification factor: baseline ES [0 or 1])	Available data on the primary endpoint will be listed.

SECONDARY ENDPOINTS			
6.3.2	Change from baseline in C-reactive protein (CRP) and fecal calprotectin (FCP) up to Week 48	The mean treatment difference between the filgotinib 100 mg q.d. group and 200 mg q.d. group at all postbaseline visits up to Week 48, using a linear mixed effects model	The available CRP and FCP data will be summarized as observed by treatment group, by visit.
6.3.2	Change from baseline in IBDQ at Week 48	The adjusted mean difference between the filgotinib 100 mg q.d. group and 200 mg q.d. using an analysis of covariance (ANCOVA)	The available IBDQ subscores and total score data will be listed.
6.3.3	Time to PRO2 flare	Estimate outcome differences between treatment groups using a Cox proportional hazards model	Listing with event details will be provided
6.3.3	Time to ES-confirmed flare	Estimate outcome differences between treatment groups using a Cox proportional hazards model	Listing with event details will be provided

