6.4	Frequency and severity of treatment-emergent adverse events (TEAEs), treatment-emergent SAEs, and TEAEs leading to treatment discontinuation.	Safety data will be summarized descriptively by treatment group according to the filgotinib dosing regimen actually received at randomization. For the primary safety analysis, any data collected after ES-confirmed UC flare will not be included in the analyses. For the secondary safety analysis, data will be included regardless of flare.	Only the primary safety analysis will be conducted. Vital signs and ECG data will be listed

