6.4.1.1. Definition of Treatment-Emergent Adverse Events

The analysis of AEs will be based on treatment-emergent events (TEAE). A TEAE is defined as

A TEAE is defined as

- An AE having a start date equal to or after the date of the first administration of study drug in this study and no later than 30 days after last administration of study drug.

- And is either a newly reported event, or a worsening^b of an existing event. Improvements are not considered treatment-emergent.

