6.4.2.7. Worst-Case Principle

Toxicity Grades

The worst-case post-baseline toxicity grade 0, 1, 2, 3 or 4 will be determined per subject, per laboratory test (and sense, if below and above), using all non-missing post-baseline records (including unscheduled and follow-up visits, but excluding local lab results).

The worst-case toxicity grade is the highest toxicity grade scored for the laboratory test (in each sense, if below and above).

Non-graded Abnormalities

The following worst-case post-baseline abnormalities L, N or H will be determined per subject, per laboratory test , using all non-missing post-baseline records (including unscheduled and follow-up visits, but excluding local lab results):

- L = low: at least one post-baseline result is classified as L.
- N = normal: all post-baseline results are classified as N.
- H = high: at least one post-baseline result is classified as H.

If, for a subject, both L and H are reported, the subject will be counted twice in the table: once with a worst-case L and once with a worst-case H.

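### SAP Table 5 drops the protocol's regardless-of-flare safety analysis, so TEAEs starting after ES-confirmed flare are listed but not counted by arm, and the laboratory rules as written do not follow the same cut

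*SAP*

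**What the plan says.** Protocol 9.3.5 defines a primary safety analysis without data collected after ES-confirmed flare, and a second one: "For the secondary safety analysis, data will be included regardless of flare". SAP 6.1, Table 5, sets out both and then states: "Only the primary safety analysis will be conducted". The reason given in SAP 6.1 is the termination and the abbreviated report. The same section keeps safety in scope: "it was decided to limit the analyses to the primary and secondary efficacy endpoints and safety endpoints". Protocol section 9 requires: "Any deviations from the CSP are to be justified in the SAP".

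The retained safety endpoint (SAP 2.1) is "Frequency and severity of treatment-emergent adverse events (TEAEs), treatment-emergent serious AEs (SAEs), and TEAEs leading to treatment discontinuation". SAP 6.4.1.1 lets a TEAE start from first dose to "no later than 30 days after last administration of study drug", with no flare limit. For the AE tables, SAP 6.4.1.8 states: "The analysis will focus on AEs reported during the treatment phase up to the time of ES-confirmed flare". AEs outside that period are listed, and so are serious AEs, deaths and AEs leading to study drug discontinuation.

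For laboratory data, SAP 6.4.2.7 derives the worst case "using all non-missing post-baseline records (including unscheduled and follow-up visits, but excluding local lab results", and SAP 6.4.2.9 analyses abnormalities over the treatment phase. Neither mentions flare.

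**The concern.** Flare does not end treatment. A subject with an ES-confirmed flare moves to open-label 200 mg for at least 12 weeks (SAP 2.2), so events can occur in time that the SAP itself calls treatment-emergent. The by-arm counts stop before that time.

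Discontinuation is the most exposed part of the endpoint. Non-response to re-escalation is a listed reason for permanent discontinuation (Protocol 5.4.1.1) and can only arise after flare. If such a stop is recorded as an AE leading to discontinuation, or as a worsening of one, the table does not count it.

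The cut can also act unequally. Under SAP 4.5.3 the denominator for event data is all subjects in the analysis set and phase. The numerator closes at each subject's flare. If one arm flares more, its counting window is shorter while its denominator is unchanged.

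The laboratory tables raise a different problem. A programmer who follows Table 5 would remove post-flare values. One who follows 6.4.2.7 and 6.4.2.9 would keep them. AE and laboratory tables in the same report could then cover different periods.

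**Working it through.** The plan attaches no figure to this point, so the check sets the passages side by side and adds simple arithmetic.

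**1. Periods covered**

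| Place | Period | Flare cut |
|---|---|---|
| Protocol 9.3.5, primary safety analysis | up to flare | yes |
| Protocol 9.3.5, secondary safety analysis | regardless of flare | no |
| SAP Table 5 | primary only | yes |
| SAP 6.4.1.1 (TEAE) and Table 1 (treatment phase) | first dose to last dose + 30 days | no |
| SAP 6.4.1.8, AE tables | treatment phase up to flare | yes |
| SAP 6.3.2, CRP and FCP tables | up to flare, later values listed | yes, stated |
| SAP 6.4.2.7, laboratory worst case | all post-baseline records | none stated |
| SAP 6.4.2.9, laboratory abnormalities | treatment phase | none stated |
| SAP 6.4.1.7 and 6.4.1.9, AEI and EudraCT tables | TEAEs | not restated |

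An event that starts on open-label treatment after flare is a TEAE by 6.4.1.1 but is outside the counts of 6.4.1.8.

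**2. Weight of one subject.** SAP 2.4.3 gives 22 randomized and SAP 2.5 gives 1:1. Arm sizes are not given, so 22 / 2 = 11 per arm is assumed. One subject whose only qualifying event starts after flare changes that arm's percentage by 1/11 = 9.1 points. With 12 in the arm it is 1/12 = 8.3, and with 10 it is 1/10 = 10.0.

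**3. Time left out.** For a subject who completes 12 weeks of re-escalation and then stops: 12 × 7 = 84 days on drug. Adding the 30-day tail gives 84 + 30 = 114 days. SAP 4.3.2 ends the last phase at last contact. If that is the 4-week follow-up visit, the figure is 84 + 28 = 112 days. Earlier termination shortens it, and continuing on open-label drug lengthens it.

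**4. Laboratory draws.** SAP 2.4.2 schedules hematology and chemistry at re-escalation Weeks 4, 8 and 12, after the switch to open-label drug.
- Worst-case tables, read literally: all three draws count.
- By-window summaries: SAP 4.3.3 keeps only the value closest to the target day in each window. Weeks 4 to 12 span 56 days, or at most 56 + 3 + 7 = 66 with visit tolerances. The narrowest window that could lie between two others is Week 12 (days 58 to 127). Draws in three windows would need one by day 57 and one from day 128, a span of at least 128 − 57 = 71 days. Since 66 < 71, at most two of the three draws can enter.
- Example: re-escalation on day 110 gives draws on days 138, 166 and 194, all in the Week 24 window (128 to 211). Only day 166, three days from target day 169, would be used.

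Groups are shown as randomized (SAP 4.5.1), so these values would sit in 100 mg rows for subjects randomized to 100 mg.

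**The case against.** The strongest reply is that the change is open and reasoned. Table 5 shows both protocol analyses and says which one stays. SAP section 1 explains that too few subjects rolled over and that the decision to stop followed consultation with the regulator. The analysis kept is the protocol's primary safety analysis, and a pre-flare count is a clean comparison of the randomized doses. After flare both arms receive open-label 200 mg, so a regardless-of-flare table mixes doses in the 100 mg row. With 22 subjects, the listings can be read by hand.

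Most of this stands, and it limits the weight. Two things remain. The stated reason explains why model-based efficacy estimates were given up. It does not explain dropping a count table for an endpoint that stays in scope. And the dose mixing was already part of the secondary analysis that the protocol planned.

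On laboratory data, Table 5 can fairly be read as governing all safety data, since the same row also disposes of vital signs and ECG. The worst-case wording may then only say which record types count. Study-specific programming rules are in a separate document that is not available here. A reader might therefore infer that post-flare laboratory values will certainly be tabulated, or that all three re-escalation draws reach every laboratory table. The documents support neither. They support a conflict of wording that has to be settled.

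**Conclusion.** The point holds with modest weight. The regardless-of-flare safety analysis is dropped openly but with only a general reason. As a result, TEAEs, serious TEAEs and TEAEs leading to discontinuation that start after ES-confirmed flare have no by-arm count. The pre-flare tables are incomplete for the retained endpoint. A reader might infer that they are wrong or that events are hidden. That does not follow, because the tables deliver the protocol's primary safety analysis and the later events are listed.

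The laboratory sections conflict with Table 5 as written. AEI and EudraCT tables do not restate the cut, although Table 5 and 6.4.1.8 can be read to cover them.

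The size is unknown because flare counts are not given. If nobody flared, the two sets of AE tables are identical. Otherwise each omitted subject is worth 9.1 points with an assumed 11 per arm (8.3 to 10.0 for 12 to 10 per arm). About 112 to 114 days are left out for a subject who completes 12 weeks of re-escalation and then stops.

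**What to change.** 1. Run the 6.4.1.8 summary table, which already carries serious TEAEs and TEAEs leading to discontinuation, and the serious-TEAE frequency table by randomized arm for all TEAEs under 6.4.1.1, regardless of flare. Place them beside the pre-flare tables and footnote that post-flare time is on open-label 200 mg.
2. Reconcile 6.4.2.7 and 6.4.2.9 with Table 5 by stating one flare rule for the laboratory tables, as 6.3.2 does for CRP and FCP.
3. Label each safety table (AE, AEI, EudraCT, laboratory) with the period it covers.

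The cost is a rerun of the existing AE programs without the flare filter and a sentence in each safety section. The downside is a few more sparse tables in an abbreviated report, in which 100 mg rows mix blinded 100 mg and open-label 200 mg time.

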Subjects will be requested to attend the site for at least 2 screening visits. Depending on the results of FCP (if applicable) and ES at screening, the subject will either be a screening failure (FCP $>250 \mu\text{g/g}$ or ES >1) in the present study and will remain in SELECTION-LTE, or the subject will be eligible (FCP $\leq 250 \mu\text{g/g}$ and ES ≤ 1) and will need to perform the End of Treatment (EoT) assessments in SELECTION-LTE before being randomized to the present study. Subjects who fail screening in the present study may be re-screened once. Re-screening may only be conducted after approval from the sponsor's medical lead.

Flare

When a subject experiences an increase in clinical symptoms, a stool sample will be obtained for culture for pathogenic bacteria, ova and parasite evaluation, and *Clostridium difficile* toxin assay.

An endoscopy will be performed in subjects who experience during treatment an increase in clinical symptoms defined as:

- an increase in rectal bleeding subscore by at least 1 point, AND an increase in stool frequency subscore by at least 2 points, AND a *Clostridium difficile* infection is excluded.

An ES-confirmed UC flare is defined as:

- an increase in rectal bleeding subscore by at least 1 point AND an increase in stool frequency subscore by at least 2 points AND an increase in endoscopic subscore by at least 1 point.

Subjects who experience an ES-confirmed UC flare during treatment will be “re-escalated” (see [Definition of Terms](#)) to open-label 200 mg filgotinib q.d. for at least 12 weeks, while maintaining the blind for the treatment at randomization, and should follow the Schedule of Activities after re-escalation. An ES-confirmed UC flare should be reported as an adverse event (AE).

Re-escalation

- In case of further worsening of symptoms after Week 2 following re-escalation and/or no improvement in pMCS is detected at Week 4, addition of corticosteroid treatment (i.e. orally- and/or rectally-administered corticosteroids) can be considered with a maximum oral dose of 30 mg q.d. prednisone equivalent.
- If the subject does not respond to re-escalation therapy within a timeframe of maximum 12 weeks, the subject will be permanently discontinued from the treatment and invited to remain in the study up to Week 48.

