4.5.3. Calculation of Percentages

Frequencies and percentages will be generated for categorical parameters.

For event-type data (e.g. adverse events), the denominator will be all subjects in the analysis set and analysis phase. For other data (e.g. worst-case analysis of assessments), the denominator will be all subjects with non-missing data for the parameter, in the analysis set and analysis window/phase.

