6.2.6. Exposure to Study drug and Compliance

6.2.6.1. Derivation Rules

Derived Parameters: Extent of Exposure to Study Drug

- *Total treatment duration* (days) = last study drug administration date – first study drug administration date + 1 day.
- *Total treatment duration, fully compliant* (days): Number of days with study drug administration, as planned per CSP.

Derived Parameters: Compliance

- Overall compliance (%) = $100 \times \frac{\text{number of doses actually used}}{\text{number of doses that should have been used}}$
- Percent days fully compliance (%) = $100 \times \frac{\text{total treatment duration,fully compliant}}{\text{total treatment duration}}$

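### Adverse-event tables stop at ES-confirmed flare but keep every treated subject in the denominator, so percentages for non-flare events run low in whichever arm flares more

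*SAP*

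**What the plan says.** - **Event window.** SAP 6.4.1.8: "The analysis will focus on AEs reported during the treatment phase up to the time of ES-confirmed flare". For later events: "Any AEs reported outside of that period will be listed".
- **Measure.** The same section: "All AE tables will show the number of subjects with applicable TEAEs", and "A summary table will be provided, showing the number (percent) of subjects with at least one" event of each type. Protocol 9.3.5.2 also plans numbers and percentages of subjects.
- **Denominator.** SAP 4.5.3, for event-type data: "the denominator will be all subjects in the analysis set and analysis phase". SAP 4.3.2 has a single treatment phase, from first dose to 30 days after last dose, with no separate phase before flare.
- **Exposure.** SAP 6.2.6.1 takes the last administration date minus the "first study drug administration date + 1 day". For a re-escalated subject this includes the open-label 200 mg period.
- **Analysis regardless of flare.** Protocol 9.3.5 plans a primary safety analysis without post-flare data and a secondary one that keeps them. SAP Table 5 (section 6.1) drops the second: "Only the primary safety analysis will be conducted".
- **Flare as an event.** Protocol 5.1 and SAP 2.2 require each ES-confirmed flare to be reported as an adverse event.
- **Setting.** 22 subjects were randomized 1:1 (SAP 2.4.3 and 2.5), the study stopped before anyone reached Week 48 (SAP 6.1), and safety is descriptive with no formal comparison.

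**The concern.** A subject who flares at, say, Week 10 can add nothing to the adverse-event tables after that date but counts in the denominator like a subject followed to the end. The time for which subjects are observed therefore depends on an outcome, flare, whose relation to dose is itself a secondary objective. A crude percentage compares arms fairly only when time at risk is similar.

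The rows most affected are those a reader would consult on the safety of the lower dose: infections, herpes zoster, thromboembolic events and the other events of interest in SAP Table 6. The planned tables do not show how long each arm was at risk, because the exposure figure covers a longer period than the event window. The analysis that would have provided a cross-check, the one regardless of flare, has been removed.

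**Working it through.** **The plan's own figure.** The only sizing figure is the precision of the remission difference in Protocol 9.1: a half width of 11% to 22.5% with 40 per group. Continuity-corrected Newcombe limits give 22.54 points at 50% vs 50% and 10.9 points at 100% vs 100%, so it reproduces. It says nothing about adverse events; neither document gives an adverse-event or flare rate. What follows is therefore an illustration under assumptions.

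**Model.** Constant first-event hazard a, equal in both arms; independent constant flare hazard f; common stop at T weeks; about 11 subjects per arm (22 / 2; the actual split is not stated). From an assumed 48-week risk p, the weekly hazard is −ln(1 − p)/48.

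- Crude proportion with an event before flare = a/(a+f) × (1 − exp(−(a+f)T))
- Expected time at risk = (1 − exp(−(a+f)T))/(a+f)
- Proportion with an event or a flare = 1 − exp(−(a+f)T)

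**Worked case.** 48-week event risk 30%, flare risk 10% in one arm and 30% in the other, T = 36. Then a = 0.00743, and f = 0.00220 or 0.00743.

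- Arm with fewer flares: a+f = 0.00963; 1 − exp(−0.3465) = 0.2929; crude 0.772 × 0.2929 = 22.6%; time at risk 30.4 weeks.
- Arm with more flares: a+f = 0.01486; 1 − exp(−0.5350) = 0.4143; crude 0.5 × 0.4143 = 20.7%; time at risk 27.9 weeks.
- Rate per 100 patient-years: 0.2261/30.4 × 5200 and 0.2072/27.9 × 5200, both 38.6 before rounding of inputs. The 1.9-point gap disappears once time at risk ends at flare.

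With a 60% event risk the crude figures are 48.0% and 44.3%, and both rates are 99.3.

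**Range.** Event risk 10% to 60%; flare risks 10% vs 20%, 30% or 50%, and 20% vs 40%:

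| Stop T (weeks) | Gap in crude percentage (points) | Largest gap in subjects out of 11 |
|---|---|---|
| 24 | 0.1 to 4.4 | 0.5 |
| 36 | 0.3 to 8.1 | 0.9 |
| 48 (upper bound; nobody got there) | 0.5 to 11.9 | 1.3 |

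**If the flare counts as an event.** At T = 36 and flare risks of 10% vs 30%, the any-TEAE row becomes 29.3% vs 41.4% (event risk 30%) or 53.5% vs 61.5% (event risk 60%). The arm with more flares now shows more.

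**If event hazards differ.** At T = 36 the downward gap vanishes when the non-flare hazard in the arm with more flares is 1.11 to 1.12 times higher (flare 10% vs 30%) or 1.26 to 1.31 times higher (10% vs 50%).

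**Early termination.** With equal flare risks the difference is zero at every T.

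**The case against.** Stopping at flare and reporting numbers and percentages is the protocol's prespecified primary safety analysis. Safety is descriptive. With 22 subjects the listings carry much of the abbreviated report: later events, relative days of events and flare details are all listed, so someone holding the listings could work out time at risk subject by subject. Rates with exact intervals at about 11 per arm will be wide and often based on zero events. All of this stands, and it limits the importance of the point. It does not make the tables themselves comparable.

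A reader might go further in four ways that the documents do not support.

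- *That the arm with more flares must show fewer adverse events overall.* The flare is a reportable event and may fall inside the window, in which case the any-TEAE row can reverse, as shown above.
- *That the bias favours 100 mg.* No flare rate is given for either dose. Protocol 2.1 says that remission may be maintained at a lower dose, and Protocol 2.3 reports that both doses reached significance in maintenance.
- *That early termination adds to the bias.* It shortens both randomized arms alike in expectation. Chance imbalance is possible with 22 subjects, but that is not a systematic effect.
- *That the distortion is larger.* Assuming no flares in one arm and 30% in the other, 1 event per year and 36 weeks (L = 36/52 = 0.692), full follow-up gives 1 − exp(−L) = 50.0% and flarers give 1 − 0.500/0.692 = 27.8%, so the flaring arm shows 0.7 × 50.0 + 0.3 × 27.8 = 43.3%. That 6.7-point gap needs a flare-free comparator, whereas Protocol 5.2 includes the 200 mg control because flares can occur for reasons other than dose. Counting the flare turns the same example into 0.7 × 50.0 + 30 = 65.0% vs 50.0%.

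**Conclusion.** The point holds for non-flare events. The numerator stops at flare, the denominator does not, the exposure summary covers a different period, and the analysis regardless of flare is gone. Given equal event hazards before flare, crude percentages for these events are too low in whichever arm flares more. For any TEAE, and for rows in which a flare would be coded, the direction is open until the SAP says whether the flare is included.

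The expected size is small: under one subject per arm at 24 to 36 weeks across the assumed range. This rests on constant, independent hazards, flares in both arms, and about 11 subjects per arm. It would not change a conclusion from this terminated study, but the tables can be made interpretable with data already collected.

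**What to change.** 1. In the TEAE, serious TEAE and event-of-interest tables, add by arm the patient-time at risk and the number of subjects with an event per 100 patient-years with an exact 95% CI. End time at risk at the first of the event, ES-confirmed flare, last dose + 30 days, or last contact.
2. State in SAP 6.4.1.8 whether the adverse event that records the flare is counted.
3. Add a count of subjects with TEAEs regardless of flare, by randomized arm, as a simple form of the protocol's secondary safety analysis. Label it as including open-label 200 mg time after re-escalation.

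Cost: a few sentences in the SAP, two extra columns per table and one extra count, with no new data. The downside is that the rates assume a roughly constant hazard and will be imprecise with 22 subjects, so they should accompany the percentages and not replace them.
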